***The final outcome is defined as described below***

- Ovary normal at postpartum scan, then **outcome** = benign
- Not operated on and level of certainty/confidence at postpartum scan = 1-2, then **outcome** = benign
- Not operated on and level of certainty/confidence at postpartum scan = 5, then **outcome** = malignant
- Not operated on and level of certainty/confidence at postpartum scan = 3-4, then **outcome** = uncertain
- Operated and histology = benign, then **outcome** = benign (even if surgery > 120 days after postpartum scan)
- Operated within 120 days since postpartum scan and histology = malignant, then **outcome** = malignant
- Operated > 120 days since postpartum scan AND histology = malignant AND level of certainty/confidence at postpartum scan is 4-5, then **outcome** = malignant
- Operated > 120 days since postpartum scan AND histology = malignant AND level of certainty/confidence at postpartum scan is 1-3, then **outcome** = uncertain
- Neither surgery nor postpartum scan (within 0-90 days) performed, then **outcome** = uncertain.

**Additional information**

***At every scan, irrespective of gestation or which arm of the study the patient falls under, the following are recorded in this specific order:***

***1) Subjective assessment (A-D as described above) and the following additional E-G criteria:***

- E: *Any subjective ultrasound change to adnexal mass from previous scan (five options):* 1) yes, change noted; 2) no change noted; 3) adnexal mass no longer detectable (no ovary seen); 4) adnexal mass no longer detectable with only a normal ovary seen; 5) unsure (comment to explain why).

- F: *Colour score of ovarian mass:* score 1, 2, 3, 4

- G: *If papillations present:* 1) number of papillations; 2) three orthogonal diameters of largest papillary projection i.e. height, base 1 and base 2; 3) smooth rounded papillations - yes / no; 4) colour in papillation - score 1, 2, 3, 4 (choose worst case scenario in case of multiple papillations).

**2) Modified Benign Descriptors and ADNEX model variables.**

***Modified Benign Simple Descriptors and ADNEX model variables will be recorded for all arms of the study but will not be used when deciding on management (Appendix 1).***

***Images of all four descriptors variables are shown and selected by ticking. The ultrasound ADNEX model variables are listed and filled in as per IOTA website and application. To ensure minimum inference, they will be recorded on a separate page from the subjective assessment on the computer software programme (Clinical Data Miner, CDM).***

***Modified Benign Descriptors and ADNEX model will not be used to guide management - only subjective assessment of the expert scanner. Therefore, participating ultrasound examiners are asked NOT to calculate the risk of malignancy using ADNEX, because the management decision should not be influenced by the results of ADNEX.***

***CA125 must be measured at the 11-14 week scan and-at the inclusion scan if done before 11 weeks OR after 14 weeks. It should be done within two weeks (+/- two weeks) of the scan - this must be prior to surgery, if surgery has been arranged.***

***If found to be pregnant again at the 0-90 days postpartum scan, the outcome will be recorded in the same manner as described above. The patient can be recruited again as a separate case, but only if the patient has presented with a new cyst.***

Retrospectively from the notes and patient's history, complications such as torsion and rupture that may have occurred will also be recorded.

### ***6.3 Definition of level of ultrasound experience***

The level of ultrasound experience is based on the number of gynaecological scans in non-pregnant women that the examiner has performed at the start of the study. Basic experience is defined as <500 scans, intermediate experience as 500-5000 scans, and expert experience as >5000. In addition, we also record other information related to experience: the EFSUMB classification and the number of ovarian masses that the examiner has examined with ultrasound during the past year (classified as <50 (< 1 per week); 50-200 (up to 4 per week); >200 (> 4 per week)).

Only those patients where the management decision was made based on the findings of an expert ultrasound examiner will be included in the study. The management decision itself need not be made by the expert ultrasound examiner.

We advise that all scans are done by the same ultrasound examiner. If not possible, as a minimum, the images from all scans of the same patient should be **assessed** by the same ultrasound examiner.

### ***6.4 Surgical intervention***

Surgery will be performed according to local protocols and the lead clinician for the patient. The reason for surgery, for example, symptoms, suspected torsion or cyst rupture or concern for malignant potential, will be recorded as part of the study. The tumour should be removed as per clinical practice. All histology will be reported and collected as per clinical practice and histology results will be documented for the study (**Appendix 5**).

### ***6.5 Study Closure***

We aim to recruit approximately 855 pregnant patients from 19 tertiary referral centres, with a minimum study duration of three years (please refer to [section 7](#)).

### ***6.6 Documentation and Communication***

Clinical data, patient demographics and ultrasound findings will be recorded prospectively in a computer software programme, acting as a web-based database (Clinical Data Miner, CDM - **Appendices 2-5**). This is a secured data collection software, dedicated for p-IOTA downloaded on password secured hospital computers. Data after entry are locked and cannot be changed.

The flow will be as follows: patient history, initial ultrasound scan, follow-up ultrasound scans, mass complications during pregnancy and surgical findings if applicable.

#### *General procedures*

Upon inclusion in the study, written informed consent is obtained from the patient. First, clinical information about the patient is entered into CDM, including information related to gestational age at time of scan and whether the mass was known before pregnancy. Second, the ultrasound examiner provides a diagnosis based on subjective assessment and enters the Modified Benign Simple Descriptors and ADNEX model variables directly after. The Modified Benign Simple descriptors and the ADNEX models are not used to decide on management.

#### *Clinical Information*

As the type of centre (oncological vs non-oncological centre) is a predictive variable in the ADNEX model, this information will be filled in. An oncological centre is a tertiary referral centre with a specific gynaecological oncology unit.

The ultrasound system used, ultrasound modality (transabdominal and/or transvaginal) and the name of the ultrasound examiner will be recorded. All ultrasound examiners must have passed the IOTA certification test.

**Appendix 2** outlines the specific general patient characteristics which will be recorded at the inclusion scan.

CA125 will be analysed and recorded at the inclusion scan and at the 11-14 week scan but must not be used to guide clinical management.

#### *Ultrasound examination*

We recognise that most patients will present with a solitary mass. However, a minority will have more than one on one ovary or bilaterally. Therefore, only the most suspicious non-physiological adnexal mass or physiological cyst (if the largest diameter measures 5cm or more) should be included. The chosen mass should have a unique identifier in the form of a numeral (1,2,3..) with letter 'L' or 'R' to signify side (for example, 1L or 2R) should be given to the mass so that it can be identified throughout pregnancy and hence avoid errors. That label should also be written on the ultrasound image so as not to confuse masses in the same ovary with each other at follow-up scans. In case of two similar masses, the one with the largest dimension or most easily accessible with ultrasound should be selected for inclusion.

A standardised transvaginal (supplemented with transabdominal if transvaginal is not sufficient) examination is performed. When a colour Doppler ultrasound examination is performed, the pulse repetition frequency should be 0.3-0.6 KHz. The colour Doppler gain should be increased until colour Doppler artefacts appear and then lowered until just below the reappearance of colour Doppler artefacts. Ultrasound frequency and "priority" (grey scale or colour/Power Doppler) must also be optimised when using colour/power Doppler. Doppler ultrasound should be used with all masses included, irrespective of gestational age.

#### ***Collection of ultrasound images and ultrasound volumes***

All participants will be asked to store a sufficient number of high-quality transvaginal ultrasound images/volumes of all masses. Images must be stored if they are suggestive of a malignancy, decidualisation and masses with papillary projections.

## **7. STUDY OUTCOME MEASURES**

### ***7.1 Primary Outcome Measures***

- Estimation of the false discovery rate when the ADNEX Model is applied at 11-14 weeks.

### ***7.2 Secondary Outcome Measures***

- Estimation of the false discovery rate when the 2-step strategy (i.e. Modified Benign Simple Descriptors followed by ADNEX) is applied at 11-14 weeks.
- Estimation of the false discovery rate when the ADNEX Model and the 2-step strategy (i.e. Modified Benign Simple Descriptors followed by ADNEX) are applied at any time point during pregnancy;
- Estimation of the ability of the ADNEX model and of the 2-step strategy (sensitivity, specificity, C-index, calibration intercept, calibration slope, clinical utility) to discriminate between benign and malignant adnexal masses at 11-14 weeks gestation.
- Estimation of the ability of the ADNEX model and the 2-step strategy (sensitivity, specificity, C-index, calibration intercept, calibration slope, clinical utility) to discriminate between benign and malignant adnexal masses when detected at any time point in pregnancy;
- Evaluation of change in morphology of ovarian masses throughout pregnancy based on subjective assessment;
- Evaluation of change throughout pregnancy and postpartum in number, size, colour score, and morphology of papillations based on subjective assessment.

### ***7.3 Tertiary Outcome Measures***

- Change in the ultrasound appearance of endometriomas during gestation;
- Occurrence of complications such as rupture, torsion, or malignancy during pregnancy in patients with conservatively treated masses (cumulative incidence illustrated by 'reverse' Kaplan-Meier curves).
- Comparison of the performance of ADNEX with CA125 and that of ADNEX without CA125.

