### ***6.2 Study flow***

**Figure 1-3** illustrate the study flow.

**First arm (*primary objective - figure 1*):** Adnexal mass scanned at 11-14 weeks. If the decision is to manage the adnexal mass conservatively, the patient is to be re-scanned once more: 0 - 90 days postpartum. In addition, the patient will be asked to enter into the third arm of the study (see below) knowing that she can opt out from that arm at any point. If she consents to participate in the third arm, she will participate in a series of longitudinal examinations as described for the third arm.

All patients with a mass detected before 11 weeks will also be scanned at 11-14 weeks and can enter all three arms of the study. In this scenario, if more than one scan is performed during pregnancy before 11 weeks, only the first of several scans before 11 weeks will be included for the second and third arms of the study (see below).

**Second arm (*secondary objective - figure 2*):** Adnexal mass is seen for the first time during that pregnancy at any gestation. If the decision is to manage the adnexal mass conservatively, the patient is to be re-scanned once more: 0 - 90 days postpartum. For patients with a mass detected before 11 weeks, see also above (they will be re-scanned at both 11-14 weeks and at 0-90 days postpartum).

In addition, the patient will be asked to enter into the third arm of the study (see below) knowing that she can opt out from that arm at any point. If she consents to this, she will participate in a series of longitudinal examinations as described for the third arm.

**Third arm (*secondary objective - figure 3*):** Patients from the first and second arms who agree to enrol into the third arm i.e. longitudinal examination of an adnexal mass during pregnancy. For the purposes of the longitudinal evaluation, the time points for the ultrasound examination are:

- initial presenting scan if <11 weeks;
- 11-14 weeks;
- 16 week scan - endometriomas ONLY;
- second trimester routine scan (18-22 weeks);
- 30-34 weeks;
- any additional scans during pregnancy which resulted in either conservative management with extra scans or surgical intervention (with reason for the extra scan or for surgery documented);
- 0-90 days postpartum.

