***If the decision is to operate after the scan at which the mass was first detected during pregnancy with no follow-up scans planned before surgery, the patient is included in the study with the final outcome being the histopathological diagnosis of the surgically removed mass (see next section).***

***If the adnexal mass is not seen at a subsequent follow-up scan but has been replaced with a normal ovary, there is no need for further follow-up scans. The final outcome is benign.***

***Patients enrolled into the study but who suffer miscarriage, ectopic pregnancy or intra-uterine death can be included in the study using same criteria as above.***

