**Management data**

- Suggested management: “What type of management do you propose for this patient based on ultrasound subjective assessment?”
  - Conservative management with one further ultrasound performed 0-90 days post-partum;
  - Conservative management with longitudinal follow-up as specified in the protocol (third arm of study - if patient consents to this);
  - Conservative management but with additional scans to the one listed in third arm of study with reason (pop-up: change in morphology, change in size, suspicion of malignancy; symptoms; other: specify);
  - Surgery by a gynaecologist or general surgeon;
  - Surgery by an oncological surgeon;
  - Mass is no longer present and only a normal ovary is seen - end of follow-up and completion of study;
  - Other, specify.

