### Complications from the mass during pregnancy?

Yes/No (pop up list) with number of episodes (one pop up per episode):

- Acute pain
- Chronic pain
- Suspected torsion
- Pelvic infection
- Cyst rupture with haemorrhage (ultrasound diagnosis)
- Cyst rupture without haemorrhage (ultrasound diagnosis)
- Underwent surgery for a mass-related incident but mass not removed  
    If Yes - type of surgery and findings:
  - Other, please specify: ....

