### Surgery (give option for more than one option)

- Gestational age at surgery or number of days postpartum when surgery done
- Type of operation:
  - Laparotomy with vertical incision
  - Laparotomy with horizontal incision
  - Operative laparoscopy
  - Diagnostic laparoscopy
  - Robotic surgery
  - Biopsy followed by neo-adjuvant chemotherapy (NACT)
  - Other (specify.....)
- Surgery performed:
  - Cyst drainage
  - Cystectomy/tumour resection
  - Oophorectomy
  - Salpingectomy
  - Salpingo-oophorectomy
  - Hysterectomy with cystectomy/tumour resection
  - Hysterectomy with salpingo-oophorectomy
  - Hysterectomy with oophorectomy
  - Hysterectomy with salpingectomy
  - Adhesiolysis

- Biopsy
- Other: specify.....
  
- Indication for operation (more than one possibility may be ticked):
  - Suspicion of malignancy based on ultrasound
  - Suspicion of malignancy based on other information; if so, which?
  - Acute / chronic pain
  - Suspected torsion
  - Suspected cyst rupture
  - Patient request
  - Increase in size of the tumour
  - Indicated by other imaging technique (suspicion of malignancy or torsion/haemorrhage/rupture)
  - Opportunistic removal of the mass when patient was operated for another indication
  - Opportunistic removal of the mass during a C/Section
  - Other: Specify: ....
  
- Findings at operation (more than one option may be ticked):
  - No tumour found
  - No complications of the tumour
  - Torsion of mass
  - Rupture of mass
  - Inflammation/Infection
  - Adhesions
  - Bleeding from tumour
  - Disseminated carcinosis
  - Omental cake
  - Other complications of tumour: specify: ....
  - Other non-gynaecological pathology (e.g. appendicitis): specify: ....
  
- Complications (intra-operative, 0-30 days, >30 days post-operative; more than one option may be ticked) with specification on when complication occurred:
  - Conversion from laparoscopy to laparotomy
  - Bowel perforation
  - Bleeding requiring transfusion
  - Pulmonary embolism or deep venous thrombosis
  - Wound-related issues
  - Urine infection
  - Chest infection
  - Pre-term labour and delivery
  - Fetal complications (specify)
  - Other: Specify: ....
  
- Histological diagnosis (pop-up list as before) with open text area ("Details"):

Benign tumour:

- Normal adnexa
- Simple cyst
- Functional cyst
- Haemorrhagic corpus luteum cyst
- Endometrioma
- Teratoma (benign)
- Fibroma
- Thecoma
- Serous cystadenoma
- Mucinous cystadenoma
- Serous cystadenofibroma

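### Section 7.3 shows complication incidence by 'reverse' Kaplan-Meier, which overstates torsion and rupture if women are censored at resolution of the mass; unoperated episodes known only from notes have no onset date

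*Protocol*

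**What the plan says.** Section 7.3 lists complications as a tertiary outcome, to be shown "in patients with conservatively treated masses (cumulative incidence illustrated by 'reverse' Kaplan-Meier curves". Three other parts of the Protocol bear on that curve.

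- **Exit by resolution.** Under 6.2, once a follow-up scan shows a normal ovary in place of the mass, "there is no need for further follow-up scans. The final outcome is benign". The management options in Appendices 3 and 4 label this state "Mass is no longer present and only a normal ovary is seen - end of follow-up and completion of study".
- **Exit by removal.** Among the surgical indications in Appendix 5 are some unrelated to a complication, for example "Opportunistic removal of the mass when patient was operated for another indication". Section 6.1 requires no study scans after surgery.
- **Timing of episodes.** Section 6.2 says that, from notes and history, "complications such as torsion and rupture that may have occurred will also be recorded". The complication block of Appendix 5 asks for "Yes/No (pop up list) with number of episodes (one pop up per episode" and prints no date or gestational age. The surgery block does ask for timing ("Gestational age at surgery or number of days postpartum when surgery done"), and the scan forms in Appendices 2 to 4 carry the date of the scan.

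The Protocol does not say how a woman whose mass resolves or is removed enters the Kaplan-Meier calculation.

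**The concern.** 1-KM equals the proportion who actually have the event only if women who are censored keep the same future risk as those still followed. A resolved mass has no remaining risk of torsion or rupture. Censoring such a woman lets the masses that persist stand in for hers, and the curve rises too far. Because the forms call the study complete at resolution, an analyst could easily take that date as the censoring date.

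The second problem is separate. A time-to-event curve needs a time for every event. An episode of suspected torsion that settled without surgery, and was learned of later from the notes, has a type and a count on the form but no time. No later analysis plan can recover a date that was never collected, and section 6.6 says that data are locked after entry.

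At stake is the description of complications under conservative management, which is a tertiary objective in section 3. An inflated torsion or rupture incidence, or one that omits untimed episodes, would misinform that description.

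**Working it through.** The Protocol gives no expected complication incidence, so there is no figure of its own to reproduce. The check compares 1-KM with the true cumulative incidence (CIF) under stated assumptions.

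**Inputs from the Protocol**
- Section 2: most first-trimester cysts resolve by 18-20 weeks, but far fewer when over 5 cm or complex. Section 5.2 excludes clearly physiological cysts under 5 cm. The resolution share in the enrolled cohort is therefore unknown.
- Section 2: torsion tends to occur at 10-17 weeks.
- Section 6.2: after 11-14 weeks the next routine study scan is at 18-22 weeks (16 weeks for endometriomas), in the third arm only. For a conservatively managed woman outside that arm, "the patient is to be re-scanned once more: 0 - 90 days postpartum".

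**Assumptions.** The cumulative risk is 2% if no mass left the risk set, so the cumulative hazard is H = -ln(0.98) = 0.0202. It is spread evenly over weeks 12-40 (28 weeks, 0.00072 per week) or weeks 12-17 (5 weeks, 0.00404 per week). The exit share r is 10, 20 or 50%.

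**(a) Exit timed individually over weeks 12-20 and censored.** The exit rate is mu = -ln(1-r)/8 per week. The CIF is the integral of lambda(t)S(t), where S(t) is the probability of neither event nor exit by t. 1-KM is 2.0% throughout.

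| r | CIF, weeks 12-40 | 1-KM / CIF | CIF, weeks 12-17 | 1-KM / CIF |
|---|---|---|---|---|
| 10% | 1.828% | 1.09 | 1.936% | 1.03 |
| 20% | 1.655% | 1.21 | 1.867% | 1.07 |
| 50% | 1.128% | 1.77 | 1.624% | 1.23 |

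For r = 50% and weeks 12-40, mu = ln 2 / 8 = 0.0866. Weeks 12-20 contribute 0.00072/(0.00072 + 0.0866) x (1 - 0.497) = 0.42%. Weeks 20-40 contribute 0.497 x (1 - exp(-0.0144)) = 0.71%. The sum is 1.13%, against 2.0%.

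**(b) Resolution seen only at a week-20 scan.** This is closer to the visit schedule. A share r resolves at week 20; a share p of women (the third arm) is censored there, and the rest stay in the risk set with no further hazard. The hazard is constant over weeks 12-40, and the CIF is [1 - exp(-8 lambda)] + exp(-8 lambda)(1-r)[1 - exp(-20 lambda)].

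| r | CIF | 1-KM, p = 1 | 1-KM, p = 0.5 | 1-KM, p = 0 |
|---|---|---|---|---|
| 10% | 1.858% | 2.000% (1.08) | 1.925% (1.04) | 1.858% (1.00) |
| 20% | 1.715% | 2.000% (1.17) | 1.842% (1.07) | 1.715% (1.00) |
| 50% | 1.288% | 2.000% (1.55) | 1.525% (1.18) | 1.288% (1.00) |

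If all events fall in weeks 12-17, before that scan, the ratio is 1.00 for every r and p.

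**(c) The condition itself.** In a simulation of 855 women (400 runs; 60% resolving over weeks 12-20, constant hazard, 5% risk without exits), 1-KM was 5.1% with censoring at resolution, against a crude incidence of 2.5%. With resolved women kept event-free to week 40, 1-KM was 2.5%. The 60% share lies outside the 10-50% range; the run shows that the bias comes entirely from the censoring rule.

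**(d) Sampling error.** 17 of 855 (2.0%) has an exact 95% CI of 1.2 to 3.2%, so the upper limit is about 1.6 times the estimate. At the 0.4% torsion plus 0.2% rupture that section 2 cites for non-pregnant women over two years, 855 x 0.006 = 5.1 events; 5 of 855 has a CI of 0.2 to 1.4%.

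**(e) Timing of events.** Operated events are timed by the surgery block, and events seen at a study scan by the scan date. What is left is the episode that was neither operated on nor seen at a study scan: mainly suspected torsion, or a rupture scanned outside the study.

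**The case against.** The strongest reply is that the Protocol states no censoring rule, and that such rules normally belong in the statistical analysis plan, which is not at hand. The word used for the curves is only that they illustrate. Section 6.2 gives a resolved mass a final benign outcome, and complications are also collected from notes, so a resolved woman can properly be carried event-free to the end of pregnancy. Working (c) shows that 1-KM is then correct. This stands: a reader might infer that the named curve is wrong as written, and the documents do not support that. What remains is that the Protocol itself names the estimator and labels resolution as completion of the study, so the choice should not be left to chance.

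The visit schedule also limits the size. The 1.77-fold figure needs resolution to be timed individually, whereas routine scans mostly detect it at 18-22 weeks or postpartum, after the torsion window. A reader might infer a large bias from the statement that most first-trimester cysts resolve; the same section and the exclusion criteria say that this rate does not carry over to the enrolled masses.

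For removal, the outcome concerns conservatively treated masses. Censoring at removal targets the risk under continued conservative management, provided that removal is unrelated to risk. Treating removal as competing targets the risk as patients were actually managed. Both are legitimate, so censoring at removal cannot be called an error.

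On dates, the Protocol prints one pop-up per episode but not the full contents of each, so the field may exist in the software. It would also be wrong to infer that complications are untimed in general; the gap is confined to the episodes in (e).

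**Conclusion.** The point holds conditionally and is minor. If women are censored at resolution, 1-KM overstates torsion and rupture incidence; if they are kept event-free to the end of pregnancy, it does not. With an assumed 2% risk and exit shares of 10 to 50%, the factor runs from 1.00 (resolution first seen after the torsion window, or only postpartum) to about 1.8 (individually timed exit, constant hazard to week 40). None of these shares comes from the Protocol, and in most scenarios the sampling error with 855 women is larger.

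The missing onset date is narrower but firmer, since analysis cannot supply it. It affects only unoperated episodes known from notes or history, and the Protocol gives no estimate of how many there will be.

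Only a tertiary, descriptive outcome is touched. The false discovery rate, the secondary accuracy outcomes and the sample size of 855 are not affected.

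**What to change.** 1. In section 7.3, replace the bracket with: 'cumulative incidence by the Aalen-Johansen estimator, with resolution to a normal ovary as a competing event for torsion and rupture (equivalently, resolved women are kept event-free to the end of pregnancy)'. The two forms agree when nobody is otherwise lost to follow-up.
2. In the same place, state whether removal of the mass for another reason is censored (risk under continued conservative management) or treated as competing (risk as actually managed).
3. In Appendix 5, add 'date or gestational age at onset' to each complication pop-up, or confirm that the software already holds it. Do this before further entry, because entered data are locked.

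The cost is one form field per episode, approximate dates where they come from history, and slightly more complex reporting. No visit, sample size or patient management changes.
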